4.2.5.5 Vital signs

Vital signs (systolic and diastolic blood pressure and heart rate) will be summarized by visit and treatment group for the safety analysis set. Observed and change from baseline values will be summarized for each visit where appropriate. This summary will be repeated by age group (< 12 years, ≥ 12 years).

Number and percentage of vital signs that are potentially clinically significant (see [Appendix 7](#)) will be summarized by parameter, category, treatment group and age group (<12 years, ≥12 years). Individual patient data for patients with marked abnormality criteria will be listed.

Vital signs parameters will be listed.

4.2.5.6 ECG

A shift table from screening Visit 1 (Week -3) to Visit 11 (Week 28/ED) will be produced showing the number and percentage of patients in each overall interpretation category (normal, abnormal not clinically significant, abnormal clinically significant) by treatment for the safety analysis set.

A listing of clinically significant abnormal ECGs will be produced.

4.2.5.7 Height

Baseline values (and percentiles), the values (and percentiles) at each visit and changes from baseline values (and percentiles) will be summarized by actual treatment during the randomized period for both the Safety analysis set and for Safety follow-up analysis set.

Height at all visits will be listed.

4.2.5.8 Tanner pubertal assessment

A shift table of change in pubertal stage from baseline Visit 3 (Week 0) will be produced for the safety analysis set (to Week 28, and each intermediate visit) and for the safety follow-up set (to up to 3-years, and each intermediate visit).

Each pubertal assessment category (pubic hair – females, breasts – females, pubic hair – males genitals – males and overall) will be summarized separately.

A listing of Tanner pubertal stage data will also be provided.

4.2.6 Pharmacokinetic analyses

The PK analysis set is defined in Section [2.1.6](#).

The exclusion of any patients from the PK analysis will be agreed by the study physician, statistician and PK Scientist during the data review meeting (DRM). The exclusion of concentration data from the PK analysis for an individual time point will be documented by the PK Scientist including the reason(s) for exclusion. These individual concentration data will be listed.

Plasma exenatide concentrations will be listed.

4.3 Conventions

All visits scheduled during the 28-week treatment period should occur within ± 7 days of the scheduled date relative to Visit 3 (Week 0) per the CSP. All visits during the safety follow-up period should occur within 6 months ± 2 weeks of the previous visit.

Patients do not always adhere strictly to the visit timing in the CSP. Therefore, the designation of visits during the treatment period will be based on the day of evaluation relative to the start of the treatment period (day of study medication = Day 1) rather than the nominal visit recorded in the CRF. Designation of visits during the safety follow-up period will be based on the day of evaluation relative to the last date of the treatment period (Visit 11/ED).

To assign a measurement to a Week t during the study, the first step is to select all measurements falling within the study period. Mutually exclusive relative day windows are used to determine the Week t measurement. These relative day windows are defined to provide derived visits that correspond to the post-baseline time points specified in the CSP. Visit windows are listed below.

4.3.1 Visit assignments for efficacy variables

Selection of SMBG measurements is discussed in section 4.2.4.4.

Table 5 Visit Windows: HbA1c

Visit	Week	Period	Target Day	Day range
3	0	TP	1	Baseline
5	4	TP	29	2-56
7	12	TP	85	57-112
9	20	TP	141	113-168
11	28	TP	197	169-last day of TP

TP: Treatment period.

Table 5 Visit Windows: FSG, FSI, HOMA-B and HOMA-S

Visit	Week	Period	Target Day	Day range
3	0	TP	1	Baseline
11	28	TP	197	2-last day of TP

TP: Treatment period.

Table 6 Visit Windows: Failure to maintain glycemic control

Visit	Week	Period	Target Day	Day range
3	0	TP	1	Baseline
4	2	TP	15	2-21
5	4	TP	29	22-42

Visit	Week	Period	Target Day	Day range
6	8	TP	57	43-70
7	12	TP	85	71-98
8	16	TP	113	99-126
9	20	TP	141	127-154
10	24	TP	169	155-182
11	28	TP	197	183-last day of TP

TP: Treatment period.

4.3.2 Visit assignment for safety variables

Table 7 Visit Windows: Antibodies to exenatide and vital signs

Visit	Week	Period	Target Day	Day range
3	0	TP	1	Baseline
5	4	TP	29	2-56
7	12	TP	85	57-112
9	20	TP	141	113-168
11	28	TP	197	169-last day of TP

TP: Treatment period.

Table 8 Visit Windows: Body weight, height, BMI and Tanner pubertal assessment

Visit	Week	Period	Target Day	Day range
3	0	TP	1	Baseline
5	4	TP	29	2-56
7	12	TP	85	57-112
9	20	TP	141	113-168
11	28	TP	197	169-last day of TP
801	+26	SFU	+183	last day of TP+1-273
802	+52	SFU	[contact]	+78	SFU	[contact]	+104	SFU	[contact]	+130	SFU	[contact]/ED	+156	SFU	+1093	1002-last day of SFU

TP: Treatment period. SFU: Safety follow-up period (+ denotes relative to Visit 11/ED)

Table 9 Visit Windows: Laboratory data, ECG, waist circumference and hip circumference

Visit	Week	Period	Target Day	Day range
3	0	TP	1	Baseline
11	28	TP	197	2-last day of TP
801	+26	SFU	+183	last day of TP+1-273
802	+52	SFU	[contact]	+78	SFU	[contact]	+104	SFU	[contact]	+130	SFU	[contact]/ED	+156	SFU	+1093	1002-last day of SFU

TP: Treatment period. SFU: Safety follow-up period (+ denotes relative to Visit 11/ED). Only CEA and calcitonin measured during SFU

Table 10 Visit windows: Hypoglycemic episodes

Visit	Week	Period	Target Day	Day range
3	0	TP	1	Baseline
4	2	TP	15	2-21
5	4	TP	29	22-42
6	8	TP	57	43-70
7	12	TP	85	71-98
8	16	TP	113	99-126
9	20	TP	141	127-154
10	24	TP	169	155-182
11	28	TP	197	183-last day of TP

TP: Treatment period.

Collected at clinic visits but discussed during telephone visits

4.3.3 Rules for safety observations

4.3.3.1 Multiple safety assessments

The assessments for laboratory parameters will be based only on central laboratory values if results for both local and central labs exist.

For the baseline visit window see section 3.6.1. For other visit windows rules below apply.

For laboratory efficacy parameters, if a patient has more than one measurement (scheduled or unscheduled) included within a relative day window, the assessment closest to the target day and time (the target time is always assumed to be 8:00 am) will be used. In case of ties between observations located on different sides of the target day and time, the later assessment will be used. In case of ties located on the same side of the target day and time (i.e. more than 1 value for the same day and time), the mean of the values will be used.

For non-laboratory efficacy parameters, if a patient has more than one measurement (scheduled or unscheduled) included within a relative day window, the assessment closest to the target day will be used. In case of ties between observations located on different sides of the target day, the later assessment will be used. In case of ties located on the same side of the target day (i.e., more than 1 value for the same day), the mean of the values will be used.

4.3.3.2 Adverse events at patient level

When a patient has the same adverse event, based on SOC/PT, reported multiple times in a single analysis period, the patient will only be counted once at the SOC/PT level in adverse event frequency tables.

When a patient has the same adverse event, based on preferred terminology, reported multiple times in a single analysis period, the following criteria, in order of precedence, will be used to select the event to be included in summary tables:

1. Relationship to study medication
2. Intensity of event
3. Onset date and time

When assessing relationship to study medication, relationship is reported by the Investigator into 2 categories - related and not related. Related events will take precedence over not related events in determining the event to include in summary tables.

More intense events will take precedence over less intense events in determining the event to include in summary tables.

Earlier onset date-time events will take precedence over late onset date-time events in determining the onset to include in summary tables.

When reporting adverse events by intensity, in addition to providing a summary table based on the event selection criteria detailed above, summary tables will also be provided based on the most intense event during the analysis period - independent of relationship to study medication. For these tables, the following criteria, in order of precedence, will be used to select the event to be included in summary tables:

1. Intensity of event
2. Onset date and time

4.3.3.3 Adverse event at event level

At event level, each unique AE record will be counted. Unique AE record can be obtained by collapsing all AE records following a standard algorithm described below.

To ensure that multiple events for the same patient are counted accurately in the summaries, a methodology for collapsing AE records and reporting for the analysis will be followed as below. For each patient and PT, AE records will be collapsed into a single record (unique AE) when:

1. Multiple AE records have the same onset date,
2. The onset date of an event record is either the same day or 1 day later than the resolution date of a preceding event record (contiguous events),

3. The onset date of an event record is after the onset date and prior to or on the resolution date of a preceding event record (overlapping events).

The unique AE record will contain the earliest onset date, latest resolution date (if available), highest intensity, relationship (yes/no), and highest action taken in the following order (highest to lowest): drug discontinued, drug interrupted, none. In addition, the unique AE record will be classified as a SAE if at least 1 AE record was classified as a SAE and the unique AE record will be classified as requiring treatment if at least 1 AE record required treatment.

5 INTERIM ANALYSES

Three safety analyses were planned for this trial beginning when at least 25% of the patients have been randomized. To minimize the operational and statistical bias that result from performing a safety assessment, the assessment for this study were to be conducted under the auspices of a Data Monitoring Committee (DMC). The purpose of the DMC was to advise the Sponsor regarding the continuing safety of study participants and the continuing validity and scientific merit of the trial. Details regarding the safety updates are given in the Data Monitoring Committee Charter. No interim safety analyses were in fact performed.

6 CHANGES OF ANALYSIS FROM PROTOCOL

The CSP does not specify eGFR as an endpoint, nor is it provided by the laboratory. However, since eGFR could provide important information it will be derived and analyzed as stated in Section 4.2.4.5 of this SAP.

In addition to the protocol-specified analysis, hypoglycemia will be summarized by baseline sulfonylurea use (yes/no) and treatment.

No Generalized Linear Mixed Model (GLMM) analysis will be done using the binary HbA1c outcome (achieved vs. not achieved HbA1c goal) as the dependent variable.

No per-protocol analysis for supportive analyses will be done.

Due to the lack of data and extent of missing data, efficacy analyses will be pooled across the 5 µg and 10 µg twice daily exenatide doses for statistical testing (Total EBID). Thus, the Fisher Protected Testing produced for the primary analysis will not be required.

For the analysis of SMBG, pre and post measurement for the same meal (lunch/dinner) is changed to be generically 2 main meals (i.e. allowing breakfast) and changed to allow data from consecutive days to be used (as many patients had only consecutive days data recorded).

Due to lack of data, plasma exenatide concentrations and antibodies will only be listed.

8 APPENDIX

Appendix 1 Study schedule – treatment period

LY2148568

Study Schedule, Protocol H8O-MC-GWBQ

Visit	1 [‡]	2	3	4 [‡]	5	6 [‡]	7	8 [‡]	9	10 [‡]	11	UV [†]	ED
Time relative to Visit 3 (weeks)	-3	-1	0	2	4	8	12	16	20	24	28		
Visit Interval (± weeks) [†]	1	1	0	1	1	1	1	1	1	1	1		
Informed consent/assent ^{**}	X												
Patient number assigned	X												
Randomization			X										
Dispense study drug/injection pen		X	X		X		X		X				
Collect study drug			X		X		X		X		X		X
Collect injection pen			X								X		X
Dispense glucose meter/supplies		X											
Instruct on glucose meter		X											
Instruct on hypoglycemia		X											
Instruct on/reinforce lifestyle modification plan [‡]		X	X	X	X	X	X	X	X	X	X		X
Placebo injection demonstration under staff supervision ^b		X											
Telephone contact				X		X		X		X			
Injection/pen training		X											
Clinical assessments:													
ECG (12-lead) ^c	X										X		X
Medical history	X												
Height ^d	X	X	X		X		X		X		X		X
Waist/Hip circumference ^e	X		X								X		X
Weight/SBP/DBP/HR	X	X	X		X		X		X		X		X
Physical examination	X										X		X
Pubertal Assessments	X	X	X		X		X		X		X		X
Concomitant medications	X	X	X	X	X	X	X	X	X	X	X		X

(continued)

Study Schedule, Protocol H8O-MC-GWBQ (Continued)

Visit	1 [§]	2	3	4 [‡]	5	6 [‡]	7	8 [‡]	9	10 [‡]	11	UV [†]	ED
Time relative to Visit 3 (weeks)	-3	-1	0	2	4	8	12	16	20	24	28		
Visit Interval (± weeks) [*]	1	1	0	1	1	1	1	1	1	1	1		
Clinical assessments (continued):													
Adverse events/Pre-existing conditions ^f	X		X	X	X	X	X	X	X	X	X		X
Distribute study diaries/food and exercise worksheets		X	X		X		X		X				
Collect study diaries/food and exercise worksheets			X	X	X		X		X		X		X
Transfer diary information to eCRF:													
Pre- and 2-hr post-prandial glucose ^g			X								X		
Hypoglycemic episodes ^h			X	X	X		X		X		X		X
Injectable therapy dose (day prior to visit) ⁱ											X		X ^j
OAD dose (day prior to visit)			X	X	X		X		X		X		X
Date of first dose of study drug recorded			X										
Date of final dose of study drug recorded											X		X
Remind patient to fast prior to next clinic visit		X								X			
Laboratory assessments^k:													
Hematology			X								X		X
Chemistry	X		X								X		X
Stored Samples			X								X		X
Pregnancy test ^l	X	X	X	X	X		X		X		X		X
Fasting C-peptide	X												
Fasting insulin			X								X		X

(continued)

LY2148568

Study Schedule, Protocol H8O-MC-GWBQ (Continued)

Visit	1 [§]	2	3	4 [‡]	5	6 [‡]	7	8 [‡]	9	10 [‡]	11	UV [†]	ED
Time relative to Visit 3 (weeks)	-3	-1	0	2	4	8	12	16	20	24	28		
Visit Interval (± weeks) [*]	1	1	0	1	1	1	1	1	1	1	1		
Laboratory Assessments^k(continued):													
Fasting glucose	X		X								X	X [†]	X
Random (non-fasting) glucose												X [†]	
Urinalysis	X		X								X		X
Hemoglobin A _{1c}	X		X		X		X		X		X		X
Calcitonin			X								X		X
CEA			X								X		X
Glutamic acid decarboxylase (GAD65) antibodies ^m	X												
Islet cell antigen (ICA512) antibodies ^m	X												
Antibodies to exenatide ⁿ			X	X	X		X		X		X		X
Patient Summary											X		X

Perform procedure as indicated unless time interval is shaded.

Abbreviations: CEA= carcinoembryonic antigen; eCRF = electronic case report form; DBP = diastolic blood pressure; ECG = electrocardiogram; ED = early discontinuation visit; HR = heart rate; OAD = oral antidiabetic drug; SBP = systolic blood pressure; UV= unscheduled visit due to loss of glycemic control; X = performed at this visit.

- A qualified person (i.e. registered dietitian (RD) or certified diabetes educator (CDE)) will introduce and reinforce the lifestyle modification program to the patient on an individual basis beginning at visit 2. At Visit 2 patients will receive 3 food and exercise worksheets that are to be completed and returned at Visit 3. At each subsequent clinic visit, the patients will be given new diaries and worksheets. Beginning at Visit 3, and continuing at each subsequent clinic or telephone visit, the RD/CDE will reinforce the lifestyle modification program with each patient until the study is complete.
- Patient (or parent or guardian) will administer a single placebo dose using the study device under the supervision of study site staff for instruction purposes only.

(continued)

- c ECGs will be performed locally.
- d Patient's height will be measured without shoes, with a wall mounted stadiometer.
- e The patient should be standing with their feet 25-30 cm apart, with their arms hanging naturally at the sides. The measurer should stand to the side of the patient, and fit the tape snugly around the waist on bare skin. Take the measurement at end-expiration with the measuring tape positioned in a horizontal plane (horizontal to the floor) at the level of the top of the bony iliac crest (minimum waist). The hip circumference should be measured at the widest area of the buttocks.
- f At visit 1, only pre-existing conditions will be collected. Pre-existing conditions will not be collected at any other visit.
- g Patient should complete and record self monitored blood glucose testing on 3 days in the week prior to clinic Visits 3 and 11.
- h Hypoglycemic episodes will be collected at all clinic visits (beginning at Visit 3). They will be discussed during the telephone visits
- i Patients should not administer injectable therapy (exenatide or placebo) prior to visiting the study site on the day of visit.
- j Only applies if the early discontinuation occurs at or after Visit 4 or any subsequent visit.
- k Patients should fast about 8 hours prior to visiting the study site on the day of visit 3 and visit 11.
- l Pregnancy test to be administered to females of childbearing potential. The pregnancy test performed at Visit 1 will be a serum pregnancy test. All tests performed at subsequent clinic visits will be urine pregnancy tests performed locally.
- m A positive result will be reconfirmed by a second test at screening, as false positives have occurred.
- n Blood samples will be collected for antibodies to exenatide analysis. Samples that test positive for antibodies to exenatide may be subjected to further immunologic characterization.
- * All procedures are to be completed prior to next visit.
- ** Patients who are 17 years of age at the time of screening that reach age of majority (as applicable in their country) during the study will be asked to re-consent.
- ‡ Visit 1 may take place in 2 different dates to accommodate the fasting procedure. If a patient comes for visit 1 non-fasting then the site will request the patient return in a fasting state within a week to draw the fasting blood glucose and c-peptide.
- † Visits 4, 6, 8, and 10 are telephone visits where the LMP is reinforced and all adverse events and concomitant medications will be documented.
- † At the unscheduled visit (UV) associated with loss of glycemic control, fasting or non-fasting glucose testing will be done locally, at which time the investigator will decide whether the patient will begin early discontinuation procedures or continue in the trial.

Appendix 2 Study schedule – long-term safety follow-up period

Study Schedule, Protocol Addendum H8O-MC-GWBQ(4) – Safety Follow-Up Period

Visit (at intervals of approximately 6 months ± 2 weeks) ^a	801	802	803	804	805	806	ED
Informed consent/assent ^b	X						
Clinical Assessments:							
Height ^{c,d}	X	X	X	X	X	X	X
Weight	X	X	X	X	X	X	X
Tanner pubertal assessment	X	X	X	X	X	X	X
AESIs	X	X	X	X	X	X	X
Ongoing prescription medications	X	X	X	X	X	X	X
Laboratory Assessments ^e :							
Calcitonin	X	X	X	X	X	X	X
CEA	X	X	X	X	X	X	X
Patient Summary ^f						X	X

Abbreviations: AESIs = adverse events of special interest; CEA = carcinoembryonic antigen; ED = early discontinuation.

- a All procedures are to be completed prior to next visit.
- b Required only for patients previously completing the protocol who have returned to the clinic for evaluation.
- c Patients will continue to return to the clinic at 6-month intervals for safety evaluation for up to 3 years or until the difference between 2 consecutive height measurements is less than 5 mm (whichever occurs first).
- d Patient's height will be measured without shoes, with a wall-mounted stadiometer.
- e Assayed by Sponsor-designated laboratory.
- f Patient Summary will be completed at the visit where the difference between 2 consecutive height measurements is less than 5 mm if this criterion occurs before the 3-year period ends.

Appendix 3 Partial date conventions for AEs

Missing type	Action
If only the day part of the AE onset date is missing	If the month and year are the same as that of first dose of study medication, the date of first dose of study medication will be used as the onset date of the AE. Otherwise, the first day of the month will be used to complete the onset date of the AE
If the day and month parts of the AE onset date are missing	If the year is the same as that of the first dose of study medication, the date of the first dose of study medication will be used as the onset date of the AE. Otherwise, January 1 st will be used to complete the onset date of the AE.
If the AE onset date is completely missing and end date missing, or after first dose of study medication	The date of the first dose of study medication will be used as the onset date of the AE.
If only the day part of the AE end date is missing	The last day of the month will be used to complete the end date of the AE.
If the day and month parts of the AE end date are missing	December 31 st will be used to complete the end date of the AE.
If the end date of the AE is completely missing and the AE is not ongoing, and the onset date of the AE occurs after the date of the first dose of study medication,	Then the onset date of the AE will be used as the AE end date. Otherwise, the date of the first dose of study medication will be used as the AE end date.

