#### **11.2.8.2. Adverse Events**

Adverse events will be summarized by presenting patient incidence and event frequency in each system organ class and in each preferred term defined by the Medical Dictionary for Regulatory Activities (MedDRA®), by treatment. Adverse events will be collected if they occur during or after the administration of randomized study medication at Visit 3 (Week 0) through study completion (Week 28) or early termination, if applicable.

Adverse events will be summarized as treatment-emergent adverse events. Treatment-emergent adverse events will be defined as those occurring on or after randomization or worsened through study completion, and will be analyzed by treatment and summarized. Adverse events that occur on or after Visit 2 (Week -1) through Visit 3 (Week 0) will be classified as pretreatment (non-treatment-emergent) and will be listed only. All adverse events will be listed by patient, visit, preferred term, treatment arm, severity, and relationship to the treatment. The frequency and percentage of treatment-emergent adverse events will be presented for each treatment arm.

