4.2.5 Safety analyses

4.2.5.1 Adverse events

Adverse events (AE) will be classified in accordance to the MedDRA dictionary. All adverse events will be coded using the latest available version of MedDRA by the database lock.

AEs starting (or worsening) after Week 28/ED but considered by the Investigator as clinically significant and as related to study medication or study procedure, and serious adverse events (SAE) occurring within 30 days of the last administration of study medication will be recorded on the AE CRF and reported in the AE listing.

Treatment-emergent AEs (TEAE) are defined as AEs starting (or worsening) after the first dose of study medication through the end of the treatment + 1 day (or + 30 days for SAEs and other clinically significant or related AEs), including AEs collected after patients initiate glycemic rescue therapy. For patients who discontinue study medication before Week 28, the end of the treatment refers to the date of the ED visit even if last study medication was before this date.

Adverse events with a start date prior to the first administration of study medication will be classified as pre-treatment (non-treatment emergent) and will be listed only.

Post-treatment AEs are defined as AEs that start (or worsen) during the off-treatment period (safety follow-up period) defined as the day after the Visit 11 (Week 28/ED) + 1 day (or + 30 days for SAEs and other clinically significant or related AEs) to the date of completion of the safety follow-up period. As per protocol only adverse events of special interest (AESIs) will be collected in long term extension.

On-treatment AEs (TEAEs) will be summarized for 28-week treatment period as defined below.

An overall summary of number and percentage of patients experiencing at least 1 TEAE will be presented for EBID and PBO. The AE summary will include the number and percentage of patients experiencing any AE, any SAE, any AE possibly related to study drug, study procedure or study device as judged by the investigator, any AE leading to treatment discontinuation, and any fatal AE.

Additionally, all TEAEs will be summarized for each treatment group as follows:

- AEs summarized by SOC, PT, intensity (Mild, Moderate, Severe), possibly related to study drug (No, Yes) and outcome
- SAEs summarized by SOC and PT, intensity (Mild, Moderate, Severe), possibly related to study drug (No, Yes)
- AEs leading to treatment discontinuation (DAE) summarized by SOC and PT

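### Two partial-date rules in SAP Appendix 3 move an adverse event that ended before dosing onto the first dose date, where it is counted as treatment-emergent

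*SAP*

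**What the plan says.** SAP Appendix 3 has three rows for incomplete onset dates.

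- **Day missing:** "If the month and year are the same as that of first dose of study medication, the date of first dose" becomes the onset; otherwise the first of the month is used.
- **Day and month missing:** "If the year is the same as that of the first dose of study medication, the date of the first dose of study medication" becomes the onset; otherwise 1 January is used.
- **Whole date missing:** the first dose date is used under a condition, "If the AE onset date is completely missing and end date missing, or after first dose of study medication".

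For an end date with the day missing, "The last day of the month will be used to complete the end date of the AE". If the month is missing too, 31 December is used.

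SAP 4.1.3.3 uses these imputed dates to decide each event's status and to tabulate it, while listings show dates as recorded. SAP 4.2.5.1 then classifies by start date: "Treatment-emergent AEs (TEAE) are defined as AEs starting (or worsening) after the first dose of study medication through the end of the treatment", and "Adverse events with a start date prior to the first administration of study medication will be classified as pre-treatment". Protocol 11.2.8.2 says of the lead-in: "Adverse events that occur on or after Visit 2 (Week -1) through Visit 3 (Week 0) will be classified as pretreatment". Those events are to be listed only.

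**The concern.** The two rows that hold some onset information use less of the recorded evidence than the row that holds none. If the end date shows that an event was over before any randomized drug was given, its onset must also be earlier. The day-missing and day-and-month-missing rows ignore this and place the onset on the first dose date.

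The same SAP handles medications differently. Appendix 4 completes a partial start with the earliest possible date, and a stop date before study drug makes the medication pre-treatment.

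The events at stake are those of the one-week placebo lead-in, when patients self-inject placebo (Protocol 6.1.2). A reaction to a lead-in injection that resolved before randomized dosing could be reported as emerging on randomized treatment.

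**Working it through.** The plan gives no figure on this point, so there is none to reproduce. The check applies the Appendix 3 rows as written.

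**1. Does each rule check the end or stop date?**

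| Rule | End or stop date checked? |
|---|---|
| Appendix 3, onset day missing | No |
| Appendix 3, onset day and month missing | No |
| Appendix 3, onset wholly missing | Yes, but no rule if the end is on or before first dose |
| Appendix 4, medications | Yes |

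Neither SAP 4.1.3.3 nor SAP 4.2.5.1 adds a check. The allowance for worsening does not help, because an event that has ended cannot worsen later.

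**2. Day missing.** First dose 20 May, lead-in from 13 May, onset May (day unknown), recorded end 16 May. Month and year match first dose, so onset = 20 May. Onset minus end = 20 − 16 = 4 days, so the event starts after it finished.

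**3. Day and month missing.** First dose 15 March 2018, onset 2018 only, recorded end 12 March 2018. The year matches, so onset = 15 March, 3 days after the end.

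**4. Incomplete end dates.** Keep first dose at 15 March 2018.

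- End in March, day unknown: imputed end 31 March. The event is treatment-emergent, but the dates are not reversed and nothing recorded proves that it ended before dosing.
- Onset 2018 only, end in February, day unknown: imputed end 28 February, imputed onset 15 March. The dates are reversed.

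The fault therefore needs an end date, recorded or imputed, that falls before first dose.

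**5. Is an onset on the first dose date treatment-emergent?** It is not literally after first dose, as SAP 4.2.5.1 requires, but it is not before it either, and an imputed date has no clock time. SAP 3.6.6 starts the treatment period on the date of first dose and ends the pre-treatment period before that date. Protocol 11.2.8.2 counts events from randomization onward. Treatment-emergent is the natural reading.

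**6. How often do the rows misfire, given such a record?** Take each of the 365 first-dose dates in a year. Let the event start *a* days and end *b* days before first dose, with 1 ≤ *b* ≤ *a* ≤ 7. That gives 28 pairs per date, and 365 × 28 = 10,220 pairs.

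- *Day missing.* A pair escapes only if its start lies in the previous month, so first dose must be on day *d* = 1 to 7. The number escaping is 28 − *d*(*d* − 1)/2, that is 28 + 27 + 25 + 22 + 18 + 13 + 7 = 140 per month, and 12 × 140 = 1,680 per year. Misclassified: 10,220 − 1,680 = 8,540 (83.6%).
- *Day and month missing.* Only starts in the previous year escape: 140. Misclassified: 10,220 − 140 = 10,080 (98.6%).
- *With an end-date condition added to both rows:* 0 of 10,220 in each case.

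These shares assume complete end dates, evenly spread first-dose dates and equal weight for every pair. They are conditional on such a partial date occurring.

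**The case against.** Setting an uncertain onset to first dose is a common cautious choice, and it is sound where the timing is truly unknown. It does not cover a record whose own end date settles the question.

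The better objection is that the trigger is narrow. A site must know when an event ended but not the day it began, usually within a one-week lead-in. Diaries are issued at Visit 2 and reviewed from Visit 3 (Protocol 6.1.2), and Protocol Section 10 provides for computer edits and a database quality review. None of this amends the rule, but it makes such records uncommon. That stands.

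Four stronger readings are tempting and are not supported:

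- **That reversed dates would distort reported durations.** SAP 4.2.5.1 plans no summary of event duration, and listings show unimputed dates.
- **That the event-collapsing rules in SAP 4.3.3.3 would fail generally.** They act only when a patient has another record of the same preferred term. In the May example, a second record starting on 25 May meets none of the three conditions and correctly stays separate. A wrong merge needs a same-term record starting on 20 May, or an earlier-starting one that resolves on 19 May or later.
- **That one arm would be favoured.** Everyone receives placebo in the lead-in, before randomization, so the expected effect follows allocation.
- **That 83.6% or 98.6% measures how many events are affected.** Both describe the rule's behaviour once such a record exists.

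**Conclusion.** The rule is wrong as written, and the consequence is minor. An event with a partial onset that matches first dose, and an end date before first dose, receives an onset later than its own end. It is then counted as treatment-emergent when Protocol 11.2.8.2 would have it listed only.

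The number of affected records cannot be worked out from the documents and is probably small. The expected result is a slight inflation of treatment-emergent counts in every arm, in proportion to allocation. Event collapsing could be affected only where the patient has another record of the same term. The primary efficacy analysis is not touched.

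The conclusion rests on treating an onset on the first dose date as treatment-emergent, which is the natural rather than the literal reading of SAP 4.2.5.1. On a strictly literal reading the event would fall into neither class, which would also need correcting.

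**What to change.** In Appendix 3:

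1. In the day-missing and day-and-month-missing onset rows, use the first dose date only if the event's end date, as recorded or as imputed under Appendix 3, is missing or on/after first dose. Otherwise impute the first day of the known month, or 1 January, so that the event stays pre-treatment.
2. In the wholly-missing row, replace the present condition, which covers only an end date after first dose, with the same on/after wording.
3. In that row, add that a wholly missing onset with an end date before first dose is classified as pre-treatment.

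Events with a missing end date, or one on or after first dose, keep the cautious assignment. The cost is a clause in each row and about a line of code; no new data are needed. A query for records whose imputed onset falls after their end date would show how many are affected under the first two rows.
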